#### 10.4 Other Safety Endpoints

Vital signs and clinical laboratory values will be presented as outlined in [Appendix E](#).

The following additional safety endpoints will be presented:

- The number of usage of hypertensive medications added after first dose by study period/visit.

The separate MACE SAP will describe the methodology for the adjudicated analyses.

### 11 SUBGROUPS

Descriptive summary statistics for the primary and secondary efficacy endpoints will be presented separately in the following subgroups of the Randomized Population. The methods for analysis will be those described for the respective primary and secondary endpoints. When

## Statistical Analysis Plan AKB-6548-CI-0014 and AKB-6548-CI-0015

analyzing a subgroup that is itself a stratification variable, it will be removed from the analysis model. These studies will enroll subjects from many centers; however, most centers will have small sample sizes. Therefore, no center-specific analyses are planned. In addition, stratification variables may be removed from the models in case of small sample size for a subgroup. A table will summarize the distribution of subjects by each subgroup and treatment group.

*Randomization stratification factors*

- Hb stratification level at baseline
  - CI-0014
    - <9.5 g/dL
    - ≥9.5 g/dL
  - CI-0015
    - <10.0 g/dL
    - ≥10.0 g/dL
- Region (actual according to CRF)
  - US
  - EU
  - ROW
- NYHA CHF stratification level
  - 0 and 1
  - 2 and 3
- Target Hb level: These targets are completely confounded with region. The 10 to 11 g/dL target consists of subjects from the US while the 10 to 12 g/dL target applies to the EU and the ROW.
  - 10 to 11 g/dL
  - 10 to 12 g/dL

*Demographics and medical history*

- Age
  - <65 years
  - ≥65 years
- Sex
  - Male
  - Female
- Race
  - White
  - All others
- Diabetes mellitus
  - No diabetes mellitus
  - Diabetes mellitus

## Statistical Analysis Plan AKB-6548-CI-0014 and AKB-6548-CI-0015

- Hypertension
  - No Hypertension
  - Hypertension
  - Medications (CI-0015 only)
- Baseline ESA dose (See Locatelli, 2004 for justification of the choice of cut-off values)
  - $\leq 90$  U/kg/week
  - $>90$  and  $<300$  U/kg/week
  - $\geq 300$  U/kg/week

*Baseline laboratory measurements*

- Urine albumin-to-creatinine ratio (uACR) – reference for cutoff: Gansevoort, 2011.
  - $<300$  g/kg
  - $\geq 300$  g/kg
- Estimated GFR – The threshold of 15 represents a value between CKD eGFR stages 4 and 5
  - $<15$  mL/min/1.73m^2
  - $\geq 15$  mL/min/1.73m^2
- C-reactive protein. In Q2 laboratories, which are the labs used in these studies, the normal range is 0 to 0.6 mg/dL.
  - $\leq 0.6$  mg/dL
  - $>0.6$  mg/dL
- Baseline TSAT
  - $<$  median of Baseline TSAT (%)
  - $\geq$  median of Baseline TSAT (%)
- Baseline ferritin
  - $<$  median of baseline ferritin (ng/mL)
  - $\geq$  median of baseline ferritin (ng/mL)

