A number of large, prospective, randomized controlled trials in CKD (Stages 3 to 5) have explored the potential benefit of ESAs in patients with CKD with respect to overall mortality, cardiovascular (CV) events, and progression of CKD with higher Hb targets (≥ 13 g/dL) ([Besarab et al. 1998](#); [Drüeke et al. 2006](#); [Singh et al. 2006](#); [Pfeffer et al. 2009a](#); [Pfeffer et al. 2009b](#)). These trials did not demonstrate the expected beneficial effects of correcting anemia on these outcomes, but suggested an increased risk of death and CV events when targeting higher Hb levels ([Besarab et al. 1998](#); [Drüeke et al. 2006](#); [Singh et al. 2006](#); [Pfeffer et al. 2009a](#); [Pfeffer et al. 2009b](#)). Additional analyses from these trials suggest that the risk of death or CV events appears to be highest in CKD patients who fail to respond to ESAs, as indicated by lower achieved Hb levels and higher average ESA dose requirements ([Szczzech et al. 2008](#); [Solomon et al. 2010](#)). This suggests that in some subjects the ESAs themselves, and not the Hb level, may be causative of the increase in events. This is supported by studies in CKD patients on dialysis with naturally high Hb levels and no increase in CV events ([Goodkin et al. 2011](#)).

The risks identified with ESAs from these trials have led to changes in prescribing information and practice guidelines in the US, the EU, and Japan that guide clinicians toward more cautious use of ESAs and targeting lower Hb levels. In the US, the mortality and CV risks associated with ESAs are outlined in a black-box warning in the prescribing information of ESAs with a recommendation to use the lowest dose possible to avoid transfusions. While no similar major warnings exist in the EU Summary of Product Characteristics (SmPC) or on the approved labeling for ESAs in Japan, the EU SmPCs for ESAs do suggest caution with the use of these drugs, with a recommendation to keep Hb levels below 12 g/dL, while the Japanese practice

guidelines recommend ESA treatment be reduced or interrupted if the Hb exceeds 12 g/dL in patients with CVD or complications. Further, recent EU clinical practice guidelines ([Locatelli et al. 2013](#)) recommend that risk factors for stroke (including a past history of stroke) and the presence of active malignancy or a past history of malignancy should be taken into account when making decisions to use ESAs for the treatment of anemia.

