## 5 SUBGROUPS

The effects of vadadustat compared to darbepoetin alfa on the incidence of the primary safety outcome will be examined across the following subgroups. All subgroup analyses are regarded as exploratory.

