### 5.1 Prespecified Subgroups

The main MACE analysis will be presented separately within the following subgroups. In each case, if the subgroup is a stratification factor or a covariate (indicated in italics), the model will be the same as the overall model with the deletion of the respective stratification factor or covariate. Subgroup analyses will be performed only if the total number of outcomes in a stratum, combined over the two treatment groups, is at least 100.

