#### *Randomization stratification factors*

- Hb stratification level at baseline
  - PRO2TECT
    - Low level group (<9.5 g/dL for CI-0014; <10.0 g/dL for CI-0015)
    - High level group (≥9.5 g/dL for CI-0014; ≥10.0 g/dL for CI-0015)
  - INNO2VATE
    - Low level group (<9.5 g/dL for CI-0016; <10.0 g/dL for CI-0017)
    - High level group (≥9.5 g/dL for CI-0016; ≥10.0 g/dL for CI-0017)
- Region
  - US
  - EU
  - ROW
- NYHA CHF stratification level
  - 0 and 1

- 2 and 3
- Target Hb level: These targets are completely confounded with region. The 10-11 g/dL target consists of subjects from the US while the 10-12 g/dL target applies to the EU and the ROW.
  - 10-11 g/dL
  - 10-12 g/dL

*Demographics and medical history*

- Age
  - <65 years
  - ≥65 years
- Sex
  - Male
  - Female
- Ethnicity
  - Hispanic
  - Non-Hispanic
- Race
  - White
  - All others
- Diabetes mellitus
  - No diabetes mellitus
  - Diabetes mellitus
- History of cardiovascular disease (defined as medical history of coronary artery disease, myocardial infarction, stroke, or heart failure as captured by four separate questions on the Case Report Form)
  - Yes
  - No
- For CI-0016 and CI-0017 only, type of dialysis

- Hemodialysis
- Peritoneal dialysis

*Medications (CI-0015 and CI-0017 only)*

- Baseline ESA dose (See Locatelli, 2004 for justification of the choice of cut-off values)
  - <90 U/kg/week
  - ≥90 U kg/week
  - >300 U/kg/week

*Baseline laboratory measurements*

- For CI-0014 and CI-0015 only, urine albumin creatinine ratio (uACR) (See Gansevoort, 2011 for a justification of the choice of cut-off values)
  - <300 mg/g
  - ≥300 mg/g
- For CI-0014 and CI-0015 only, estimated GFR (The threshold of 15 represents a value between CKD eGFR Categories 4 and 5)
  - <15 ml/min/1.73m^2 (CKD Stage 5)
  - ≥ 15 ml/min/1.73m^2 (CKD stage 4 or lower)
- C-reactive protein. In Q2 laboratories, which are the laboratories used in these studies, the normal range is 0-0.6mg/dL.
  - ≤0.6 mg/dL
  - >0.6 mg/dL
- Baseline transferrin saturation (TSAT)
  - CI-0014 and CI-0015
    - < median of CI-0014 and CI-0015 combined
    - ≥ median of CI-0014 and CI-0015 combined
  - CI-0016 and CI-0017
    - < median of CI-0016 and CI-0017 combined
    - ≥ median of CI-0016 and CI-0016 combined
- Baseline ferritin

- CI-0014 and CI-0015
  - < median of CI-0014 and CI-0015 combined
  - $\geq$  median of CI-0014 and CI-0015 combined
- CI-0016 and CI-0017

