  - < median of CI-0016 and CI-0017 combined
  - $\geq$  median of CI-0016 and CI-0017 combined
- Incident Dialysis Patients
  - CI-0016 and CI-0017
    - All patients in CI-0016 plus patients who have  $\leq 16$  weeks of dialysis history from the date of informed consent in CI-0017
- Pooled analysis of patients with CKD G5 and incident dialysis patients (those who initiated dialysis within 16 weeks) after all studies indicated below are completed
  - <15 ml/min/1.73m^2 (CKD Stage 5) at baseline from CI-0014 and CI-0015
  - All patients in CI-0016 plus patients who have  $\leq 16$  weeks of dialysis history from the date of informed consent in CI-0017

In these summary statistics, only the primary analysis method will be presented. Hazard ratios and their 95% confidence intervals for subgroups will be displayed using forest plots.

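### The MACE SAP's baseline ESA dose subgroups overlap (<90, ≥90, >300 U/kg/week), leave out a 90-300 row and do not match the main SAP's three disjoint groups

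*SAP*

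**What the plan says.** **Main SAP (CI-0014 and CI-0015).** Section 11 gives three baseline ESA dose groups for CI-0015: ≤90, >90 and <300, and ≥300 U/kg/week. It cites a 2004 reference "for justification of the choice of cut-off values". Appendix D.3 uses the same three levels as a predictor in time-to-event models. Section 6.3.8 converts all ESA doses to IV epoetin equivalents in U/kg/week.

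**MACE SAP.** Section 5.1, under "Medications (CI-0015 and CI-0017 only)", lists <90, ≥90 and >300 U/kg/week and cites the same 2004 reference. It states: "The main MACE analysis will be presented separately within the following subgroups". It also sets a minimum: "Subgroup analyses will be performed only if the total number of outcomes in a stratum, combined over the two treatment groups, is at least 100". At the end of the section it adds: "Hazard ratios and their 95% confidence intervals for subgroups will be displayed using forest plots". Section 5 describes the status of these analyses: "All subgroup analyses are regarded as exploratory".

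**The concern.** The second MACE group is unbounded above, so it contains the whole of the third. A forest plot drawn from this list would show three rows that look like a partition but are not one. Subjects above 300 would contribute to two rows, and those at about 90 to 300 would never be shown on their own. The efficacy display for the same CI-0015 subjects would use three groups that do partition them, so the middle efficacy row would have no MACE counterpart.

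The subgroup is of some clinical interest. Protocol Section 4 reports earlier analyses in which risk appeared highest in patients who did not respond to ESAs, "as indicated by lower achieved Hb levels and higher average ESA dose requirements". CI-0015 enrols patients already on an ESA, so a reader will look at this display. Overlapping levels also cannot be coded as one classification variable, which leaves the programmer to guess what was meant.

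**Working it through.** The plan gives no figure to reproduce here. The main check is which rows each dose falls into.

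**Step 1: group membership.** Inputs are the two lists of groups from main SAP Section 11 and MACE SAP Section 5.1.

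| Dose (U/kg/week) | Main SAP row | MACE SAP row or rows |
|---|---|---|
| 50 | ≤90 | <90 |
| 90 | ≤90 | ≥90 |
| 200 | >90 and <300 | ≥90 |
| 300 | ≥300 | ≥90 |
| 450 | ≥300 | ≥90 and >300 |

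On a grid from 0 to 1000 in steps of 0.1, every dose falls in exactly one main SAP group. In the MACE SAP, doses up to 300 fall in one group and doses above 300 fall in two. If the second MACE group is capped at 300, every dose falls in exactly one group, but subjects at exactly 90 and exactly 300 are still placed differently from the main SAP.

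**Step 2: when the >300 row would appear at all.** In PRO2TECT only CI-0015 contributes to this subgroup. The current documents give the 631 events for the pair and no share for CI-0015, so the share is an assumption. I use 40% (assumed), 50% (equal planned enrolment, 1850 of 3700) and 68% (the figure in Section 11.1.2 of the superseded protocol text, which is absent from the current one).

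- 40%: 631 × 0.40 = 252 events; 100/252 = 40% of them must be above 300.
- 50%: 631 × 0.50 = 316 events; 100/316 = 32%.
- 68%: 631 × 0.68 = 429 events; 100/429 = 23%.

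So the >300 row needs about 23% to 40% of CI-0015 events to be analysed. If it is dropped, nobody appears twice, but the ≥90 row still mixes middle and high doses.

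**Step 3: what splitting the ≥90 row costs.** Let E be the events in the ≥90 row and s the share of them from doses above 300. After the split the rows hold sE and (1 − s)E events. The documents give no dose distribution, so take s = 0.40 for illustration.

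- The larger row reaches 100 when 0.60 × E ≥ 100, that is E ≥ 167.
- Both rows reach 100 when 0.40 × E ≥ 100, that is E ≥ 250.

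For E from 100 to 166 the present text yields one hazard ratio above 90 and the split yields none. For E from 167 to 249 the split yields the middle row only.

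**The case against.** The best defence is that <90 and ≥90 already form a partition, and >300 is a nested high-dose row. On that reading nothing is wrong, and dropping >300 under the event minimum leaves a clean two-row display. The text does not say that nesting was intended, and the other multi-level subgroups in that list read as partitions. Even if nesting was meant, no estimate is planned for about 90 to 300, and the rows still do not match the main SAP.

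It is also fair to say that the blinded team described in MACE SAP Section 1 could settle the grouping as a convention. That is possible, but the section does not name this case.

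Several stronger inferences are tempting, and the documents do not support them:

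- **That subjects are counted twice in an analysis.** The model is run separately in each subgroup. A subject above 300 enters two models, once each, and no total adds the rows.
- **That high-dose risk is hidden.** A separate >300 row is already listed. Only the middle row is missing, although the event minimum could remove the >300 row.
- **That efficacy and MACE results by ESA dose cannot be compared.** The low rows agree except at exactly 90 and the high rows agree except at exactly 300. Few subjects should have a converted, weight-based dose exactly on a boundary.
- **That the protocol calls high dose in itself the highest-risk state.** Its background concerns poor responders, marked by low achieved Hb together with higher dose needs, and words this as a suggestion.
- **That the ≥90 hazard ratio would be distorted by a known amount.** Any such figure needs a hazard ratio and an event share above 300 that the documents do not give.

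**Conclusion.** The point holds as an inconsistency between the two SAPs in a prespecified subgroup rule. In the MACE SAP all subjects above 300 U/kg/week fall in two rows, no row isolates about 90 to 300, and the boundary signs at 90 and 300 differ from the main SAP. This follows from the wording alone and needs no assumption.

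Its reach is limited to one exploratory display. MACE SAP Section 4.4 does not include ESA dose among the primary model's covariates, so neither the non-inferiority decision nor any formal test depends on it. The statements about which rows would clear 100 events rest on the assumed CI-0015 share of 631 events and on the illustrative share above 300. They show that rows could be lost; they do not predict which.

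**What to change.** Before database lock and unblinding, replace the ESA dose groups in MACE SAP Section 5.1 with those of main SAP Section 11 (≤90; >90 and <300; ≥300 U/kg/week), and state that the conversion in main SAP Section 6.3.8 applies. For any ESA dose row with fewer than 100 events, show event counts and rates by arm in place of the hazard ratio. Because the MACE subgroup also covers CI-0017, check that the INNO2VATE SAP, which is not among these documents, uses the same groups.

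The edit is about one line, with no effect on patients, data collection or the primary analysis. The price is the one shown in the working: one or both upper rows may fall below the event minimum, so a hazard ratio that the ≥90 row would have supplied may not be estimated. The counts and rates partly make up for that. Agreeing the grouping before unblinding keeps it independent of the results.

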**12 OTHER EXPLORATORY ANALYSES**

In addition to the planned analyses described above, the study team will likely perform many other descriptive analyses of efficacy and safety. For example, the team is likely to provide descriptions of the trajectory of subjects who transition to chronic dialysis, which will include the figures for Hb and other labs after the date of initiation of dialysis.

**13 DATABASE LOCK AND UNBLINDING****13.1 Blind Review of Selected Data Prior to Final Database Lock**

Upon database release, protocol deviation and analysis population outputs will be produced and will be sent to Sponsor for review. An analysis population classification meeting will be arranged to discuss the outputs and to decide which subjects and/or subject data will be excluded from certain analyses. Decisions made regarding the exclusion of subjects and/or subject data

Statistical Analysis Plan AKB-6548-CI-0014 and AKB-6548-CI-0015

from analyses will be made prior to unblinding and will be documented and approved by Sponsor.

The following summary of analysis population will be provided:

- *A summary of the number and percentage of subjects allocated to each analysis population by blinded treatment group and overall (Analysis population: All Subjects Randomized)*

A by-subject listing of analysis population details will be provided. This listing will be presented by blinded treatment group and include: site, subject identifier, inclusion/exclusion flag for each population and reason for exclusion from each population. All subjects randomized will appear on this listing. Other data may also be selected for blind review if deemed necessary.

### **13.2 Final Database Lock**

After completion of all Blind Data Review, validation of the project databases, and Akebia's approval of the review, the clinical database will be locked. After the database lock and the authorization for unblinding ([Section 13.3](#)), the treatment codes will be merged to the analysis datasets. Any change to the clinical database after this time will require written authorization, with explanation, by Akebia. In addition, beginning at the time of database lock, an audit trail will be maintained of all versions of the analysis datasets that may result from refinements of the algorithms for derived variables in the course of the analysis.

### **13.3 Authorization for Unblinding**

After database lock and upon receipt of written authorization from Akebia, a blinded study team will receive the actual treatment codes directly from the group maintaining them for data analysis.

## APPENDIX A. JUSTIFICATION OF THE NONINFERIORITY MARGIN

### A.1. Historical Trials for Indication

Several drugs in the erythropoiesis stimulating agent (ESA) class have been studied and approved for increasing hemoglobin (Hb) levels in subjects with anemia related to chronic kidney disease (CKD). They are, in order of FDA approval:

- erythropoietin alfa (EpoA from [Amgen, 1986](#))
- darbepoetin alfa (DA from [Amgen, 1998](#))
- Mircerca ([Roche, 2004](#))
- Omontys ([Affymax, 2007](#)).

We have combined the results of the pivotal trials leading to the approval of these agents with the results from several other studies and performed a meta-analysis of 16 study arms to estimate the placebo-adjusted change from baseline in Hb after 24 to 36 weeks of correction treatment. The growing precedence for this endpoint plus the summary treatment effect estimated here support the noninferiority margin of -0.75 g/dL used for the primary analyses in the PRO2TECT (CI-0014, CI-0015) and INNO2VATE (CI-0016, CI-0017) trials.

### A.2. Characteristics of Study Arms

The 16 study arms included (see [Table A 1](#)) vary in several key characteristics, namely: dialysis dependence (DD) or non-dialysis-dependent (NDD); the maximum allowable Hb level for inclusion of participants; the average baseline Hb level; the therapeutic drug; the timing of the primary efficacy outcome; and the target range of Hb. The timing for the PRO2TECT and INNO2VATE studies is planned for 24 to 36 weeks for the primary endpoint, and the target range of Hb is 10 to 11 g/dL in the United States (US) and 10 to 12 g/dL ex-US.

The Mircerca and Omontys trials used noninferiority margins of -0.75 and -1.0 ng/dL, respectively.

**Table A 1. Study Characteristics**

| Study Label | Drug Label a | Number Treated | Target Hb Level b | Average Baseline Hb (g/dL) | Dialysis Dependence | Reference to Literature c |
|-------------|-------------------------|----------------|------------------------------|----------------------------|---------------------|--------------------------------------|
| TREAT       | DA                      | 2012           | High                         | 10.4                       | No                  | 4                                    |
| Affymax     | OM1                     | 328            | High                         | 10.0                       | No                  | 5                                    |
| Affymax     | OM2                     | 328            | High                         | 10.0                       | No                  | 5                                    |
| Affymax     | DA                      | 327            | High                         | 10.0                       | No                  | 5                                    |
| Roche       | DA                      | 162            | High                         | 10.2                       | No                  | 3                                    |
| Roche       | MI                      | 162            | High                         | 10.2                       | No                  | 3                                    |
| Akizawa     | DA                      | 161            | High                         | 9.2                        | No                  | 6                                    |
| Akizawa     | Epo                     | 160            | Low                          | 9.2                        | No                  | 6                                    |
| Amgen202    | DA                      | 129            | High                         | 9.3                        | No                  | 1,2                                  |
| Amgen202    | Epo                     | 37             | High                         | 9.8                        | No                  | 1,2                                  |
| AmgenDial   | Epo1                    | 201            | High                         | 7.4                        | Yes                 | 7                                    |
| Amgen211    | DA                      | 91             | High                         | 8.8                        | Yes                 | 1,2                                  |
| AmgenCAN    | Epo1                    | 44             | Low                          | 6.9                        | Yes                 | 8                                    |
| AmgenCAN    | Epo2                    | 38             | High                         | 7.1                        | Yes                 | 8                                    |
| AmgenDial   | Epo2                    | 35             | High                         | 8.2                        | Yes                 | 7                                    |
| Amgen211    | Epo                     | 31             | High                         | 8.5                        | Yes                 | 1,2                                  |

CAN: Canada; DA: darbepoetin alfa; Dial: dialysis; Epo: epoetin alfa; MI: Mircera; OM: Omontys.

a. Suffixes indicate various dosing regimens.

b. The high target Hb levels range from 11 to 13.5 g/dL, and the low levels range from 9 to 11 g/dL.

c. Reference key follows.

1. Macdougall IC. Darbepoetin alfa: a new therapeutic agent for renal anemia. *Kidney Int Suppl.* 2002;61(80):55-61. doi:10.1046/j.1523-1755.61.s80.11.x.
3. Macdougall, I. C., Walker, R., Provenzano, R., de Alvaro, F., Locay, H. R., Nader, P. C., ... Investigators, A. S. (2008). C.E.R.A. corrects anemia in patients with chronic kidney disease not on dialysis: results of a randomized clinical trial. *Clin J Am Soc Nephrol*, 3(2), 337–347. <https://doi.org/10.2215/CJN.00480107>
4. 18 October 2010 CRDAC Meeting Briefing Document Epoetin alfa (EPOGEN®/PROCRT®) and darbepoetin alfa (Aranesp®) <https://wayback.archive-it.org/7993/20170403223814/https://www.fda.gov/AdvisoryCommittees/CommitteesMeetingMaterials/Drugs/CardiovascularandRenalDrugsAdvisoryCommittee/ucm192863.htm>
5. CDER, FDA. Omontys (peginesatide) BLA. [https://www.accessdata.fda.gov/drugsatfda\\_docs/nda/2012/202799orig1s000statr.pdf](https://www.accessdata.fda.gov/drugsatfda_docs/nda/2012/202799orig1s000statr.pdf). Published 2012.
